#### Assessment of the level of knowledge (primary outcome):

The level of knowledge of the patients will be assessed in the intervention group by a questionnaire (Appendix 1) on three occasions: at time 0 before any intervention as a pre-test, after the teaching interview as post-test n°1 and finally at 1 month post-discharge as post-test n°2.

This questionnaire will be proposed in the control group at time 0 (pre-test) and at 1 month after hospitalization (post-test).

During hospitalization, the questionnaire will be sent to the patient by the investigating pharmacist and will be completed by the patient himself with the help of the pharmacist if necessary.

At 1 month after discharge, the questionnaire will be sent to the patient by email or post. If no return is obtained, the research assistant will address the questionnaires to them during a phone call.

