Endpoint(s)	
Primary Endpoint:  Patients' level of knowledge about their disease and heart failure medications before the educational pharmaceutical intervention and after the intervention, as well as at 1 month after hospital discharge. It will be measured by means of a 17-question questionnaire specifically developed for this project. This level is valued by a minimum score of 0 points and a maximum of 17 points.  This criterion will also be assessed for both groups during hospitalization and at 1 month after discharge.
 
Secondary endpoints :  Beliefs about medication will be measured via the specific Beliefs about Medicine Questionnaire (BMQs) score before the intervention and at 1 month after hospital discharge.  Adherence will be assessed with the Three Item Self Report Scale before the procedure and at 1 month after discharge.  These two criteria will also be assessed in both groups, during hospitalization and at 1 month after discharge.  Patient satisfaction will be assessed directly after the teaching intervention and at 1 month after hospitalization.  The consumption of unplanned care such as re-hospitalizations, emergency medical visits will be evaluated at 1 month of hospitalization as well as the death rate at 1 month of hospitalization.  A follow-up questionnaire on the return home will allow us to identify the patient's feelings and experiences on their return from the hospital  The usability of a smartphone application, CardioMeds®, developed for heart failure patients by the University Hospitals of Geneva (HUG) will be explored at 1 month after the return home of patients who have agreed to install it on their smartphone and to use it.  Their self-care skills following the use of this mobile (smartphone) application will also be measured using a validated questionnaire.

Study Design	Single-center randomized controlled trial
Statistical considerations	
The final analysis will use an intention-to-treat analysis, including all patients who were randomized into the study.
 
Continuous variables will be expressed as means <math>\pm</math> standard deviations, median and interquartile range.
 
The categorical variables will be described by their numbers and the proportion as a percentage.

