 28 For example for question n° 2: 1 point if predefined keyword present; 0,5pt if partial keyword  
 29 but general concept correct; 0 pt otherwise.

30  
 31 The final score can vary from 0 (no knowledge) to 17 points (excellent knowledge).  
 32 The questionnaire has never been used in an experimental context or for psychometric  
 33 analysis. There is no threshold to say that a patient has good knowledge or not.  
 34 It was developed by an internal pharmacist and an assistant pharmacist trained in TVE. It is  
 35 based on educational objectives derived from educational sessions with patients and meetings  
 36 with two patient partners from the HUG (Appendix 2). It was previously evaluated with them  
 37 and on three occasions with a group of hospitalized heart failure patients (10 patients per  
 38 version of the questionnaire).

39  
 40 To determine a first basic level of knowledge of the heart failure patients hospitalized at the  
 41 HUG, the final version of the questionnaire was tested with 10 patients who had not received  
 42 any educational intervention. This analysis shows that:

- 43 • The average baseline score is 7.95 pts out of 17.00pts (with a standard deviation of  
 44 2.67) or 46.76% of correct answers;
- 45 • The median score of 8.25pts out of 17.00 pts (min. 4; max. 13) or 48.53% of correct  
 46 answers.

47  
 48 In this clinical study, we wish to assess the level of knowledge of the intervention group before  
 49 the teaching interview, directly after the teaching interview, and at 1 month after the  
 50 participant's discharge from the hospital.

51 This study includes a control group in order to evaluate the real effect of the therapeutic  
 52 teaching intervention. The level of knowledge of the control group will be evaluated at inclusion  
 53 for the pre-test and at 1 month after hospitalization for the post-test.

54

1  
2 Secondary endpoints included differences in medication belief and adherence scores and the  
3 difference in the rate of unplanned care use between the two groups at 1 month post-  
4 hospitalization.

5  
6 They also focused, for the intervention group, on the difference in belief and therapeutic  
7 adherence scores between the period before the educational intervention during  
8 hospitalization and the period following this intervention, i.e., one month after hospital  
9 discharge.

10 Four additional endpoints will be assessed after the pharmaceutical intervention with the study  

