### 3.4 Study intervention

The control group will receive the usual care offered by the internal medicine service without the therapeutic education intervention of the pharmacist during their hospitalization.

The intervention will be conducted by the pharmacist investigator with patients in the intervention group. These are heart failure patients with reduced LVEF, polymedicated, hospitalized for cardiac decompensation in the 10 general internal medicine units of the HUG. They will benefit from the usual medical care. The intervention will consist of an educational pharmaceutical interview associated with a second interview to prepare for hospital discharge (pre-discharge interview), followed by a telephone call a few days after hospital discharge.

The therapeutic education intervention that the patient will receive will be structured in three parts:

1. The first part consists of a 60-90 minute interactive edutainment session that will take place in the patient's bed. It will be carried out from the 3rd day of admission for a cardiac decompensation. The teaching is structured in two subparts, which will allow it to be carried out in one or two sessions if necessary to reduce its duration and preserve the patients' level of concentration. One or two appointments will be scheduled with the patient to ensure that they are available throughout the interview.

The teaching will address 3 themes related to the disease of heart failure: the pathology, the drugs to treat it and the self-care and self-monitoring actions to adopt. A pedagogical scenario has been designed to serve as a detailed description of the teaching and as a teaching guide for the pharmacist trainer. It is presented in the appendix (Appendix 11).

The teaching is standardized and can be used for all patients, regardless of their level of knowledge. Indeed, the elements and the games used are flexible according to the skills of the participants. The trainer will be able to vary his level of investment according to their needs, their wishes and their skills.

Below is a brief description of the elements used in this interview:

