50	Heart failure medication list (hospital discharge)	Medical record	 Diuretic  Beta-blocker  IECA/ARA  ARNI  Aldosterone antagonist (ARM)  SGLT2 inhibitor  Ivabradine  Digoxin  Vericiguat
51	Medication management in the home	Patient interview	 Autonomous  Nursing care  Pharmacy  Caregivers
52	Medication management tool	Patient interview	 Paper Medication Plan  Electronic Medication Plan  Weekly/Plus  Daily unit dose sachet  Unit discount by the pharmacy  Other
53	Frequency of visits to your regular pharmacy	Patient interview	 Several times a week  1 time per week  2-3 times a month  1 time per month  1 time every 2-3 months  2 times a year  1 time per year  Never
54	Quality of the relationship with your city pharmacist	Patient interview	 No particular relationship  Wrong  Neither good nor bad  Good  Very good
Pre-test data			
55	Knowledge Questionnaire	Patient interview	Answer for each question (detailed in the documents specific to the questionnaires)
56	Score	Calculation	Value:
57	Belief questionnaires	Patient interview	Answer for each question (detailed in the documents specific to the questionnaires)

58	Need score	Calculation	Value:
59	Concern score	Calculation	Value:
60	Differential score	Calculation	Value:
61	Membership questionnaire	Patient interview	Answer for each question (detailed in the documents specific to the questionnaires)
62	Membership score	Calculation	Value:
Post-interview FTE data (for intervention group only)			
63	Knowledge Questionnaire	Patient interview	Answer for each question (detailed in the documents specific to the questionnaires)
64	Score	Calculation	Value:

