### **Sample size**

To test our hypothesis, we need to define an adequate sample size.

To do this, we initially consulted the literature. Several studies have demonstrated an improvement in patient knowledge after pharmacist intervention with approximately 100-200 patients (45–56).

The questionnaire used to measure patient knowledge has never been studied to date. We tested it in 10 hospitalized heart failure patients who were naïve to any teaching intervention.

This analysis shows that:

- The average baseline score is 7.95 pts out of 17.00pts (with a standard deviation of 2.67), i.e. 46.7% of correct answers;
- The median score of 8.25pts out of 17.00 pts (min. 4; max. 13) is 48.5% correct answers.

By setting a relative gain of 30% as the smallest difference to be detected, this would be equivalent to showing an improvement in the mean score of at least 2.39 points ( $\pm 7.01$ ) (i.e., a mean score increase from 7.95 to 10.34pts).

Assuming a two-sided alpha of 5% and a power of 80%, 40 subjects per group should be included, for a total of 80 subjects. Considering a loss to follow-up in about 10% of the study subjects, the required sample size would be at least 90 subjects (45 subjects per group). This sample size was calculated with STATA 17 (STATA Corporation, College Station, Texas).

We also need to consider the average number of patients hospitalized at the HUG for left heart decompensation with decreased LVEF to define the inclusion time and feasibility of this project. Note that according to internal hospital statistics, the number of patients hospitalized in general internal medicine for left heart decompensation (all severities and LVEFs combined) in 2019 was 641 and 434 between January and November 2021. It is considered that 50% of these patients have a reduced LVEF, equivalent to 200-330 patients per year who could benefit from our intervention or approximately 16-25 patients per month. A certain number of these patients will not meet the inclusion criteria and a small number, approximately 30%, will agree to participate, as shown by certain studies in heart failure patients (71–74). In addition, some patients will be missed by the investigator who will only work part-time on this project.

Based on all these elements, we expect to include approximately 124 patients (62 per group) over 12 months, to show a progression of knowledge which is a sufficient number to guarantee the statistical power of the study.

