### **Planned analyses**

#### *Primary analysis*

To answer the main research question, a linear regression (or ANCOVA) will be performed to compare the estimated mean scores at 1 month between the two randomization groups after adjustment for the baseline knowledge score. For subjects for whom the knowledge score could not be obtained at post-test, we will use the baseline value as post-test value in order to avoid missing data. The threshold of statistical significance under the null hypothesis is set with a type I error,  $\alpha < 0.05$

The primary analysis will be carried out by a statistician from the Methodological Support Unit of the HUG Clinical Research Centre, who will be commissioned by the investigator once the data of the last patient included have been collected.

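### The intervention arm sits the primary-outcome questionnaire three times and the control arm twice, so the 1-month comparison mixes the pharmacist package with one extra test exposure of unknown size

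*Combined protocol and SAP*

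**What the plan says.** The outcome instrument is built for this trial and scored 0 to 17 (synopsis: "It will be measured by means of a 17-question questionnaire specifically developed for this project"). Section 4.3, on the primary outcome, gives it to the intervention arm "on three occasions: at time 0 before any intervention as a pre-test, after the teaching interview as post-test n°1", with the last sitting 1 month after discharge. For the other arm it says: "This questionnaire will be proposed in the control group at time 0 (pre-test) and at 1 month after hospitalization (post-test". Section 3.2 describes the same schedule. Table 2 lists the second in-hospital questionnaire and its score as items 63-64, under the heading "Post-interview FTE data (for intervention group only".

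Section 5.1 sets the primary analysis: linear regression or ANCOVA "to compare the estimated mean scores at 1 month between the two randomization groups after adjustment for the baseline knowledge score". Section 3.2 gives the reason for having controls: "This study includes a control group in order to evaluate the real effect of the therapeutic" teaching.

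Section 3.4 defines what is being tested: "The therapeutic education intervention that the patient will receive will be structured in three parts". These are the teaching session, the pre-discharge interview and the telephone call. The knowledge questionnaire is not one of them; section 4.3 treats it as outcome assessment. Section 3.1 also asks whether knowledge progresses after the interview and whether the level is maintained 30 days after discharge.

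**The concern.** A test can change what it measures. A patient who has just been taught and then works through the 17 items sees which facts matter and retrieves them once before the final test. Here that happens in one arm only and on the very items that form the primary endpoint. A difference at 1 month could then be read as an effect of teaching when part of it comes from the additional sitting.

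Three features of the plan add weight:

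- In hospital the questionnaire may be completed with the pharmacist's help (section 4.3), and the investigating pharmacist also delivers the teaching (section 3.4).
- Section 3.2 says the questionnaire has had no psychometric analysis, so no retest data show that the effect is negligible. The documents describe no parallel form and no sensitivity analysis.
- In section 4.3 and Table 2, beliefs and adherence are measured at the same two times in both arms. Among the questionnaires compared between arms, only the primary one has unequal exposure.

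The rise from pre-test to the immediate post-test also has no control value. A simple retest gain cannot be told apart from learning there.

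**Working it through.** **1. Count the sittings.**

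| Sitting | Intervention | Control |
|---|---|---|
| Pre-test in hospital | yes | yes |
| Directly after teaching (Table 2, items 63-64) | yes | no |
| 1 month | yes | yes |

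The synopsis says knowledge is assessed in both groups during hospitalization and at 1 month. The control pre-test already satisfies that, so it adds no second in-hospital sitting for controls.

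**2. Ask whether the analysis removes the difference.** Write the primary model as Y(1 month) = a + c × Y(baseline) + t × arm + error. Both arms sit the pre-test, so any effect of that sitting cancels. The extra sitting comes after Y(baseline) was recorded and only in one arm. Its effect b therefore enters the arm coefficient: t = package effect + b. Neither randomization nor baseline adjustment touches b.

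**3. The plan's own figure.** Inputs from section 5.1: difference 2.39 points (30% of 7.95), SD 2.67, "Assuming a two-sided alpha of 5% and a power of 80%, 40 subjects per group should be included", and 45 per group after 10% loss.

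- n per group = 2 × (1.960 + 0.842)² × SD² / difference².
- With SD 2.67: 2 × 7.849 × 7.129 / 5.712 = 19.6, so 20, not 40.
- With SD 2.67 × √2 = 3.776: 2 × 7.849 × 14.258 / 5.712 = 39.2, so 40. The documents do not state this SD.
- Loss: 40 / 0.90 = 44.4, so 45.

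The mismatch is a separate matter. It is used here only to show results under both SDs.

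**4. Size of b.** The documents give no retest gain, so b is an assumption. Set against the 2.39-point target:

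| Assumed b (points) | b / 2.39 |
|---|---|
| 0.25 | 10% |
| 0.50 | 21% |
| 0.75 | 31% |
| 1.00 | 42% |

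**5. Illustration only: chance of a significant 1-month difference if the package adds nothing and the arms differ by b.** Two-sided 5% t-test, noncentral t with 2n − 2 degrees of freedom and noncentrality b / (SD × √(2/n)). Example: n = 45, SD 2.67, b = 1.0 gives 1.0 / (2.67 × 0.2108) = 1.78 and a rate of 42.0%. SD 2.31 is 2.67 × √(1 − 0.5²), which approximates the adjusted analysis under an assumed baseline to 1-month correlation of 0.5.

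| n per group | SD | b = 0 | 0.25 | 0.50 | 0.75 | 1.00 |
|---|---|---|---|---|---|---|
| 45 | 2.67 | 5.0% | 7.2% | 14.2% | 26.1% | 42.0% |
| 45 | 3.78 | 5.0% | 6.1% | 9.5% | 15.4% | 23.7% |
| 45 | 2.31 | 5.0% | 8.0% | 17.4% | 33.1% | 52.8% |
| 62 | 2.67 | 5.0% | 8.1% | 17.9% | 34.2% | 54.3% |
| 62 | 3.78 | 5.0% | 6.5% | 11.3% | 19.5% | 31.0% |

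Reaching the expected 62 per group does not help: b stays the same while the standard error shrinks. These rates leave out the rule in sections 5.1 and 5.2 that puts the baseline score in place of a missing post-test. With 10% loss, an assumed 1.0 points averages 0.90 × 1.0 = 0.90 over the arm, so the rates would be somewhat lower.

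**The case against.** The strongest reply is that the effect may be trivial. Controls also have one prior exposure, so only the second one differs, and the final test comes a month after discharge. No section says that answers or feedback follow the immediate post-test. The package already rehearses content through a quiz, games, a memory card the patient completes, a discharge interview and a call. One more sitting is a small addition, and no retest gain in the range above is anchored in the documents. This stands as regards size. It does not remove the asymmetry, because the extra sitting uses the exact outcome items and the protocol does not declare it part of the intervention.

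A second reply is that the immediate gain is not tested: the confirmatory comparison is at 1 month. That is correct, so the missing control value affects how a stated objective is interpreted, not the primary test.

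A reader might infer from the last table that the false-positive risk is known to be seriously inflated. The documents do not support that. The rates assume that the package teaches nothing, whereas the more persuasive mechanism is retrieval of content just taught. If nothing was learned, only familiarity with the form remains. The rates also depend on the SD and ignore the baseline-carried-forward rule.

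**Conclusion.** The asymmetry is explicit and consistent across sections 3.2 and 4.3 and Table 2. The primary comparison estimates the three-part package plus one extra sitting of the outcome test, and adjusting for baseline cannot separate them. Bias towards the intervention is plausible but not demonstrated. Its size is unknown and may be small after a month: under an assumed gain of 0.25 to 1.0 points it would be 10% to 42% of the 2.39-point target. The false-positive rates are illustrations, not estimates.

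It would go too far to say that the trial cannot show an effect, or that a positive result would be an artefact. The point is a cheap improvement to make at the design stage, because after enrolment the extra sitting can no longer be separated from the teaching.

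**What to change.** Give control patients the same questionnaire a second time in hospital, at an interval after their pre-test matched to the intervention arm and with the same rule on help. The protocol should fix that interval, since the teaching lasts 60 to 90 minutes and may be split into two sessions. Move Table 2 items 63-64 to both arms, amend sections 3.2 and 4.3 to match, and report the immediate gain as a between-arm comparison.

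State in the protocol and the report what this achieves. It equalises test exposure, but untaught controls cannot retrieve newly taught material, so any benefit from that remains part of the estimated package effect.

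The cost is protocol wording and one more short form for about 45 to 62 control inpatients, using existing materials and staff. The sample size and the primary time point do not change.

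Dropping the immediate post-test would also equalise exposure and would remove the retrieval element. It is not preferred, because it would delete the section 3.1 objective of measuring progression after the interview.

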Study procedures	
Each working day, the investigator will identify all patients with heart failure with a lowered left ventricular ejection fraction (LVEF) and hospitalized for cardiac decompensation at the HUG. He will assess whether they meet the eligibility criteria for this study. The investigator or a trained clinical research associate (CRA) will come and present the study to the eligible patients by giving them the information sheet and the consent form to sign if they agree to participate. They will be given at least 24 hours to think about whether they want to participate. Once the patients are included (eligibility criteria validated and consent signed), they will be randomly assigned to the intervention or control group according to the randomization list.
 
For patients in the intervention group, the therapeutic education intervention will be scheduled on the same day or the next day. The pre-test questionnaires (knowledge, beliefs, and adherence) will be given to them before the educational intervention. The post-test questionnaires and satisfaction survey will be given to the participants directly after the intervention. A second discharge interview will be organized shortly before final discharge from the general internal medicine or cardiology department. A call within 7

	
days of discharge will be made and an assessment at 1 month of hospitalization of the primary (knowledge) and secondary (beliefs, adherence, satisfaction, consumption of unplanned care) endpoints will be made either by e-mail, postal mail, or telephone call by the CRA only.
 
For patients in the control group, the pre-test questionnaires on knowledge, beliefs and adherence will be given to them on the same day or the day after inclusion. A post-test evaluation of knowledge, beliefs, adherence and rate of consumption of unplanned care will be performed at 1 month after hospitalization.

Study duration and Schedule	
12 months
 
Planned from 09/2022 for inclusion of first participant
 
Planned to 09/2023 for inclusion of last participant

Investigator(s)	[name] candidate, HUG Pharmacy
Study Center	
University Hospitals of Geneva
 
[name]
 
[name]

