51 application on patients' level of empowerment in their care.  
52  
53

[figure not shown]
1 During hospitalization, the four questionnaires (knowledge, beliefs, therapeutic adherence,  
2 and satisfaction) will be sent to the participants in paper or electronic format (on a tablet)  
3 according to the patient's wishes by the pharmacist investigator or the research assistant.  
4 These questionnaires will be sent again to the participants at 1 month after discharge from  
5 hospital, as well as the two questionnaires for the participants using CardioMeds®. They will  
6 be sent either by e-mail or by post to be completed by the patient and returned to the  
7 investigator. In the event that these questionnaires are not returned, they will be addressed  
8 orally during a telephone interview by a research assistant.

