**Storage:**

The identification list of participants will be kept in a secure manner (see §8.2 data recording and source data)

For the duration of the study, the data will be stored in the CDMS, REDcap™, which can only be accessed by the investigator and a research assistant with a personal login and password.

All paper source data will be available in a dedicated study cabinet. This cabinet will be stored in the pharmacy's clinical trials office. All other source documents will be stored electronically, in the pharmacy's secure network, accessible only by the principal investigator and his/her research assistant.

Access to the database will be available to the study investigator and research assistant only during the inclusion process, but also during the data analysis phase and after the study is completed. Access will be password protected to prevent unauthorized access.

Once the data is collected and the REDCap™ database is complete, the data will first be extracted into an Excel spreadsheet. This will be stored in the pharmacy's secure network.

For the statistical analysis, the data of interest will be prepared for transfer to the statistician of the Methodological Support Unit, so that he can import them into the statistical software he will use. A do-file will be used to store all the statistics produced.

Where possible, we will store files in open archive formats, such as Word files converted to PDF-A or simple text files encoded as UTF-8 files and Excel files converted to CSV. If this is not possible, we will include information about the software used and its version number.

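### The teaching pharmacist also handles the in-hospital knowledge test, so the plan permits teaching to be fitted to the outcome items a patient missed

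*Combined protocol and SAP*

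**What the plan says.** **Who teaches.** Section 3.4: "The intervention will be conducted by the pharmacist investigator". That role gives the 60 to 90 minute bedside session, the interview 1 to 2 days before discharge and the telephone call between D3 and D7.

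**Who handles the test in hospital.** Section 4.3, on the primary outcome: "the questionnaire will be sent to the patient by the investigating pharmacist and will be completed by the patient himself". The form is "completed by the patient himself with the help of the pharmacist if necessary". Section 4.2 has the investigator learn the allocated arm and then collect the pre-test data. The end of section 3.2 is looser: the in-hospital questionnaires are handed over, on paper or tablet, "according to the patient's wishes by the pharmacist investigator or the research assistant".

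**When.** Synopsis, study procedures: "The pre-test questionnaires (knowledge, beliefs, and adherence) will be given to them before the educational intervention". In the intervention arm the knowledge test is repeated directly after the teaching (post-test n°1), and again 1 month after discharge. Controls take it at inclusion and at 1 month. The 1-month assessment is done by e-mail, post or telephone and is reserved to the CRA.

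**Who can see the answers.** Table 2 records the answer to each question, not only the score, at the pre-test and at post-test n°1. Section 8.3 (Storage): "Access to the database will be available to the study investigator and research assistant only during the inclusion process"; the sentence then extends access to the analysis phase and beyond.

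**How far the teaching can vary.** Section 3.4 says both "The teaching is standardized and can be used for all patients, regardless of their level of knowledge" and "The trainer will be able to vary his level of investment according to their needs, their wishes and their skills".

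**The concern.** The 1-month knowledge score is meant to show whether the education improves what patients know about their disease and medicines. It does so cleanly only if the teaching is independent of how a given patient answered the test that later serves as the outcome.

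Here one person can hand over the test, help with it, open the recorded answers, and then teach the same patient with some freedom over content. If that person goes over the questions a patient got wrong, part of the gain at 1 month is recall of those particular answers. Controls have no contact in which missed items could be corrected, so the effect would run in one direction only. It could not be removed in the analysis, because nothing in the data would record whether items were gone over. The questionnaire has had no psychometric analysis (section 3.2), so nothing shows that gains on single items reflect wider knowledge.

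**Working it through.** The point concerns procedure, so the main check is to set the steps in order.

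**1. Sequence for an intervention patient** (Synopsis; sections 3.4, 4.2 and 4.3)

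| Step | Who |
|---|---|
| Consent signed, arm revealed | Investigator |
| Pre-test, 17 items | Pharmacist (4.3), or research assistant (3.2) |
| Teaching session | Pharmacist |
| Post-test n°1, same items | Pharmacist (4.3), or research assistant (3.2) |
| Discharge interview | Pharmacist |
| Call, D3 to D7 | Pharmacist |
| 1-month test, same items (primary) | CRA only |

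The pre-test comes before all three pharmacist contacts, and post-test n°1 before two of them. A control patient goes from the pre-test to the 1-month test with none of these contacts.

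**2. Access.** Table 2 (answers by question) and section 8.3 (investigator's database access during inclusion) together mean that item answers are open to the teacher while the patient is still being taught.

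**3. Safeguards.** No visible section withholds answers or scores from the teacher, requires another person to give the in-hospital tests, or bars going through the items. The questionnaire (Appendix 1) and the pedagogical scenario (Appendix 11) are not in the text, so a rule placed there cannot be excluded. The topics listed for the test in section 3.2 and for the teaching in section 3.4 overlap closely.

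**4. Scale of the score.** The pilot mean was 7.95 of 17 (SD 2.67, 10 patients), so on average 17 − 7.95 = 9.05 points are not obtained before teaching. The target is 0.30 × 7.95 = 2.385, given as 2.39 points. With at most 1 point per question, that is fewer than three items.

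**5. Illustration of sensitivity, on assumed values.** The documents give no size for item-specific correction. Suppose it adds b points to the intervention mean at 1 month, with no wider gain in knowledge and 45 patients per group. Ignoring baseline adjustment and missing data, SE = SD × √(2/45), and the chance of a significant result favouring the intervention is P(Z > 1.96 − b/SE).

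Two SDs are shown because the plan's 40 per group does not follow from SD 2.67: 2 × (1.960 + 0.842)² × 2.67² / 2.39² = 19.6, or 20 per group. It does follow from √2 × 2.67 = 3.78, which gives 39.2, or 40. The allowance for loss reproduces: 40/0.9 = 44.4, or 45. The present point does not depend on the sample size.

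| b (assumed) | b / 2.39 | SD 2.67 (SE 0.56) | SD 3.78 (SE 0.80) |
|---|---|---|---|
| 0 | 0% | 2.5% | 2.5% |
| 0.5 | 21% | 14% | 9% |
| 1 | 42% | 43% | 24% |
| 2 | 84% | 94% | 71% |

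The table shows only that the comparison would be sensitive to a point or so. It is not an estimate of what will happen.

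**The case against.** The strongest reply is that possibility is not practice. No section says that the pharmacist marks or reads the answers before teaching. Patients fill in the form themselves, with help only when needed, and the research assistant may hand it over. The video that opens the teaching follows the pre-test, which may leave little time to mark eight multiple-answer and three keyword-scored questions. All of this stands, and it is why the point is worded as something the plan permits.

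Second, adapting to needs is part of the declared service. The Synopsis and section 2 describe education targeted on patient needs, and section 2 names knowledge assessment before discharge as a way to target them. Closing gaps found in this way is arguably the intervention itself. This stands in part. Tailoring can stay; the difficulty lies in tailoring from the instrument that is also the primary outcome.

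Third, the questionnaire derives from educational objectives that closely match the teaching topics, and a pharmacist who knows the items knows them whether or not individual answers are seen. This also stands: the fix removes only the patient-specific part.

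Fourth, the CRA alone handles the 1-month test. That protects how the primary time point is administered. It does not reach what was taught beforehand.

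The standardised scenario is a partial safeguard at most, since section 3.4 goes on to describe flexible elements and games.

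**Conclusion.** The concern holds as a risk. The teaching pharmacist may hand out and help with the knowledge test, can open its item answers before further contacts with the patient, and may adapt the teaching; no visible safeguard separates these tasks. Any resulting distortion of the 1-month difference would favour the intervention. Its size cannot be derived from the documents, and the values of b used above are assumptions.

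A reader might go further and infer that the pharmacist knows each patient's errors, will teach to them, and that the primary effect is therefore biased upwards by a stated amount. The documents do not support that. They show access and opportunity, not use; they allow someone else to hand out the forms; they treat tailoring to needs as part of the service; and the two appendices that would settle the content are not available. The average of 9.05 points not obtained is a pilot mean, not a count of errors the teacher will have seen.

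The conclusion assumes that the pharmacist investigator, the investigating pharmacist and the investigator with database access are the same role, as the protocol's use of the terms indicates.

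**What to change.** - Reconcile the end of section 3.2 with section 4.3. The pre-test and post-test n°1 should be completed by direct tablet entry or on a sealed form, or with the research assistant where available. Any help should come from someone other than the teaching pharmacist.
- Set REDCap rights so that the teaching pharmacist cannot open a patient's knowledge answers or score until that patient's 1-month form is in.
- State in sections 3.4 and 4.3, and in the pedagogical scenario if it does not already say so, that individual questionnaire answers are not used or gone through in the teaching, the discharge interview or the call. Needs are still assessed with the session's own discussion, games and quiz.

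**Cost.** A few protocol sentences and one user-right setting. The pharmacist loses the pre-test as a needs assessment. Where the research assistant is used, that person's time must be coordinated around each session, which may be split in two; section 10 says that outside funding for the CRA position is still being sought, so tablet or sealed completion is the less demanding route. The pharmacist's general familiarity with the items remains and should be acknowledged when the result is reported.
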